This cross-over study aims to investigate the impact of two metabolically distinct diets on Glycated hemoglobin, cardiovascular health, the gut microbiome, and metabolic status. Participants are recruited using media advertisements, email lists, and clinician referral ([name]) from previous recruitment for nutrition studies conducted by our laboratory group. Forty participants are planned to be randomized between the two arms: (1) start with 12 week WFKD and switch to 12 week Med-Plus; (2) start with 12 week Med-Plus and switch to 12 week WFKD. Randomization will be stratified by diabetes vs pre-diabetes status. As displayed in figure above, clinical and metabolic measurements are taken at baseline, and weeks 0, 6, 12, (Phase I, weeks 1-12), 18, 24 (Phase II, weeks 13-24) and 36 (Maintenance Phase). Continuous glucose monitoring will be collected five times during the trial, each time data will be collected every hour for ten days.

Primary Outcome:

• Difference in percent difference from baseline after 12 weeks of each phase

Secondary Outcomes:

- Difference in percent difference from baseline in LDL cholesterol after 12 weeks of each phase
- Difference in percent difference from baseline in HDL cholesterol after 12 weeks of each phase
- Difference in percent difference from baseline in triglycerides after 12 weeks of each phase
- Difference in percent difference from baseline in fasting insulin after 12 weeks of each phase
- Difference in percent difference from baseline in blood pressure after 12 weeks of each phase
- Difference in percent difference from baseline in weight after 12 weeks of each phase
- Difference in percent difference from baseline in alpha diversity after 12 weeks of each phase. Primary metric of alpha diversity will be using number of observed sequence variants ("species") determined by standard 16S rRNA amplicon sequencing (V3-V5 region followed by DADA2 to define error-corrected sequence variants). *Note: Higher alpha diversity is better. The units are the # of sequence variants*
- Difference in percent difference from baseline in composite of short-chain fatty acids (SCFA) concentration (ug/g stool: acetate + propionate + butyrate) after 12 weeks of each phase

Exploratory outcomes:

- Difference in satisfaction with WFKD and Med-Plus diets, using a 5-point Likert scale (1=not at all satisfied; 2=slightly satisfied; 3=moderately satisfied; 4=very satisfied; 5=extremely satisfied).

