- Difference in adherence to diet protocols by diabetes vs. pre-diabetes status, according to 3day food records.
- Tabulate COVID-19 Survey answers

Primary Analysis

Patient demographics and baseline clinical characteristics will be summarized by arm, as n (%) and median (interquartile range) for categorical and continuous variables, respectively. To assess any differences in each variable between the two arms, the absolute standardized differences are presented, where a value of 0.2 or less, 0.5, and 0.8 or more correspond to small, medium, and large differences, respectively. Characteristics found to display large differences will be adjusted for in a sensitivity analysis. We will also compare rate of adherence for WFKD after 12 weeks and Med-Plus diets after 12 weeks using a Fisher's Exact test with weekly NDSR (and Cronometer) data. We will develop a composite score to measure a participant's adherence to each diet.

We will use a mixed-effects linear model (1) with HbA1c percent difference from baseline for diet, j, as the outcome. We want to assess for a difference in diet (WFKD vs Med-Plus), while adjusting for fixed effects: order (e.g. study arm), pre-diabetes vs. diabetes status, and a random effect for each participant, i.

$$\left(\frac{HbA1c_{ij}-HbA1c_{i0}}{HbA1c_{i0}}\right) = \beta_o + \beta_1 Order_i + \beta_2 Diabetes_i + \beta_3 Diet_{ij} + \gamma_i$$
(1)

For the primary outcome, we will use a two-sided likelihood ratio test to test for no difference between diet types. The primary analysis will include participants with baseline blood draws, and at least one blood draw in each phase (including crossing over). The primary analysis will be a complete case analysis and use participants' last available lab values in each phase or week 12, if available; patients who did not complete both phases (i.e. crossover) will be excluded. A significance level of 0.05 is set for all analyses. In a sensitivity analysis, we will adjust for baseline weight and percent weight change if weight change from baseline is found to be significant, since this is known to impact HbA1c values; and in a separate analysis, we will adjust for adherence to each diet.

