Similarly, for our secondary outcomes, we will use separate mixed-effects models to evaluate fasting lipids, insulin, glucose, blood pressure and short-chain fatty acids for WFKD vs Med-Plus, adjusting for order, phase, pre-diabetes vs. diabetes status, and repeated measures. A two-sided likelihood ratio test will be used to assess no difference between diet types. For our exploratory outcome comparing diet satisfaction, we will use a Wilcoxon signed-rank test to evaluate the null hypothesis that the difference between pairs follows a symmetric distribution around zero, which indicates similar satisfaction with both diets. We will use a Fisher's Exact test to evaluate any difference in the rate of adherence due to diabetes vs pre-diabetes status, within each diet.

Sensitivity Analysis

Due to COVID-19, visits to collect blood draws were delayed for some participants. These participants report they maintained the phase's diet until the lab measurements could be collected. We will check adherence to diet based on NDSR at Week 12 and Week 12 extra visit (taken when allowed back into clinic), and also check for a change in dietary and exercise habits during shelter-in-place. Potential impact of delays are unclear; subsequently, we will perform a number of sensitivity analyses:

Sensitivity Analysis 1 (SA1): For a simple truncated analysis, we will consider only the first phase (12 weeks) of each group and compare differences (two-sample)

Sensitivity Analysis 2 (SA2): For a simple estimate of Week 12 analysis, we will consider the average of the last lab measurement of each 12 week phase and the extra data point at Week 12 extra visit.

Sensitivity Analysis 3 (SA3): For an extended-phase analysis, we will consider using the last lab measurement from each phase, i.e. the "extra" data timepoints after week 12 in study for some participants.

Sensitivity Analysis 4 (SA4): For a pre-COVID-19 truncated analysis, we will consider the subset of data prior to the official Shelter-in-Place date for the Bay Area, March 16, 2020.

Sensitivity Analysis 5 (SA5): To assess any effect on outcomes due to COVID-19 impact on logistics, we will consider the subset of data when participants received groceries for each diet. We will also evaluate if adherence was better for the first four weeks when groceries were delivered.

Secondary Analysis

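### The secondary outcomes are each tested at 0.05 with no multiplicity control and no descriptive label, so the chance of at least one false diet difference is up to about one in three

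*SAP*

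**What the plan says.** Three parts of the SAP bear on this.

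- **Secondary Outcomes list (under Study Design).** There are eight bullets, each a contrast between diets in percent change from baseline: LDL cholesterol, HDL cholesterol, triglycerides, fasting insulin, blood pressure, weight, alpha diversity and a short-chain fatty acid (SCFA) composite. A typical entry is "Difference in percent difference from baseline in LDL cholesterol after 12 weeks of each phase". The blood pressure entry, "Difference in percent difference from baseline in blood pressure after 12 weeks of each phase", does not say whether systolic and diastolic pressure are one outcome or two.
- **Primary Analysis, threshold.** "A significance level of 0.05 is set for all analyses".
- **Primary Analysis, closing paragraph on secondary outcomes.** "we will use separate mixed-effects models to evaluate fasting lipids, insulin, glucose, blood pressure and short-chain fatty acids for WFKD vs Med-Plus", followed by "A two-sided likelihood ratio test will be used to assess no difference between diet types".

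The SAP contains no hierarchy, familywise adjustment or false discovery rule, and does not say that secondary p-values are descriptive. It does qualify other results: under Secondary Analysis the diet-by-diabetes interaction is flagged as having little power, and under Exploratory Analysis the maintenance-phase work is described as mainly descriptive. The secondary outcomes carry no such qualification.

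**The concern.** This is not a silence that the protocol might fill. The SAP states a rule and applies it to every analysis. Under that rule any single secondary test with p below 0.05 may be called significant, however many were run.

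The stated objective is to contrast possible benefits and harms of the two diets, and the design paragraph names cardiovascular health, the gut microbiome and metabolic status beside glycated hemoglobin. Lipids, blood pressure, alpha diversity and SCFA appear only on the secondary list, so much of the stated contrast rests on tests whose joint error rate is not limited. What is at stake is overclaiming, in either diet's favour, from one chance result among several.

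**Working it through.** **Inputs from the SAP.** Per-test level 0.05, two-sided (Primary Analysis). Number of declared secondary outcomes: 8 (Secondary Outcomes list). The SAP gives no familywise error rate, so there is no figure of its own to reproduce.

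**Input assumed.** The SAP gives no correlations among outcomes. A common correlation r between test statistics is assumed and varied from 0 to 0.9.

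**Step 1: number of tests.** The declared list and the variables named for modelling do not match.

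- Variables named for modelling: lipids (LDL, HDL, triglycerides), insulin, glucose, blood pressure, SCFA = 7, or 8 if systolic and diastolic pressure are separate.
- Declared list: 8, or 9 with blood pressure split.
- Declared list with blood pressure split and glucose added: 10.

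Weight and alpha diversity are declared but not named for modelling. Glucose is named for modelling but not declared.

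**Step 2: independent tests, no true difference on any outcome.** P(at least one p < 0.05) = 1 − 0.95^k.

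- k = 7: 0.302
- k = 8: 0.337
- k = 9: 0.370
- k = 10: 0.401

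**Step 3: correlated tests, no true difference on any outcome.** Simulation of equicorrelated normal test statistics, two-sided, 400,000 draws. The r = 0 row is the exact formula from Step 2.

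| r | 7 tests | 8 tests | 9 tests |
|---|---|---|---|
| 0 | 0.302 | 0.337 | 0.370 |
| 0.1 | 0.298 | 0.333 | 0.364 |
| 0.3 | 0.272 | 0.300 | 0.326 |
| 0.5 | 0.229 | 0.249 | 0.270 |
| 0.7 | 0.178 | 0.190 | 0.203 |
| 0.9 | 0.114 | 0.119 | 0.125 |

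**Step 4: some true differences.** If the diets truly differ on four of the eight outcomes, false positives can arise only on the other four: 1 − 0.95^4 = 0.185 if independent.

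**Step 5: what adjustment does to the threshold.** With eight tests, Benjamini-Hochberg compares the i-th smallest p-value with 0.05 × i/8. The limit runs from 0.05 × 1/8 = 0.00625 for the smallest, if it stands alone, to 0.05 × 8/8 = 0.05 if all eight are small. In the least favourable case, an outcome with an assumed 80% power at 0.05 has Φ(2.80 − 2.73) = 0.53 at 0.00625. The loss is smaller when several outcomes differ. The SAP states no power, so the 80% is illustrative.

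**The case against.** The strongest case on the other side has four parts.

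1. *The one-in-three figure is a ceiling for eight tests.* A reader might take it as the expected rate. It needs independence and no diet difference on any outcome. The outcomes come from the same participants, and several (lipids, insulin, weight) are probably related. The SAP itself describes the diets as metabolically distinct, which sits poorly with no difference anywhere. This stands: the figure has to be given as an upper value with its conditions.
2. *The SAP does not name a test for each declared outcome.* This also stands. That all eight are tested follows from the general reference to secondary outcomes and from the threshold covering all analyses, not from the list of variables to be modelled. The mismatch makes the family unclear, which is a further reason to define it.
3. *The SAP ranks its outcomes.* A reader might infer from the shared 0.05 that a secondary finding would carry the same weight as HbA1c. The document does not say so: it separates one primary outcome from secondary and exploratory ones, and a common nominal level does not equate their standing. That stronger reading is not supported. The ranking still does not say how an isolated secondary p below 0.05 may be described.
4. *Strict familywise control could cost too much.* With 40 participants and an objective that includes harms, a strict rule could make adverse differences harder to flag. This is a fair argument against making Holm or Bonferroni a gate. It is not an argument against printing adjusted values beside unadjusted ones.

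It is also true that many trials leave secondary outcomes unadjusted. That is defensible when the plan says so, and this one does not.

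**Conclusion.** The concern holds as a point about the interpretation of secondary results. For eight tests the probability of at least one false diet difference runs from 34% (independent tests, no true differences) through about 25% at r = 0.5 to 12% at r = 0.9. The count could be 7 to 10, which gives 30% to 40% under independence. The correlations are assumed throughout, but no value in the range examined brings the rate near 5%, and with four real differences it is still about 19% under independence.

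A reader might infer that the trial's main conclusion is at risk. It is not: HbA1c is a single primary test at 0.05 and is unaffected. Nor do the adherence, satisfaction, interaction and sensitivity analyses enter these figures. The sensitivity analyses re-examine outcomes already tested, so counting them as further independent claims would overstate the problem. This is a change worth making, not a fatal flaw.

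**What to change.** Amend the SAP wording as follows.

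- Keep 0.05 for the primary HbA1c test and replace the blanket rule for the other analyses.
- Define the secondary family as the eight outcomes in the Secondary Outcomes list, counting systolic and diastolic pressure separately if both are tested.
- Align the modelling paragraph with that family: name weight and alpha diversity, and state that glucose lies outside the family unless it is declared.
- Report Benjamini-Hochberg adjusted p-values at a 5% false discovery rate beside the unadjusted p-values and confidence intervals for every outcome in the family.
- Describe secondary results that do not survive adjustment, and all sensitivity, subgroup and exploratory results, as hypothesis-generating.

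Benjamini-Hochberg limits the expected share of false findings among those declared. It does not hold the chance of any false finding at 5% once some differences are real. For a supportive family in a 40-person crossover that is a reasonable compromise, and the SAP should say that this is what is controlled.

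The cost is wording plus a calculation on p-values already produced. No new data, visits or participants are needed. Fewer secondary outcomes may be called significant, but all unadjusted estimates, including adverse differences, stay in view.

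### The HbA1c models adjusted for percent weight change and for adherence estimate a direct effect of diet and should not be labelled sensitivity analyses of the total effect

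*SAP*

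**What the plan says.** Model (1) in the Primary Analysis section compares the diets on percent change in HbA1c, "adjusting for fixed effects: order (e.g. study arm), pre-diabetes vs. diabetes status, and a random effect for each participant, i". For the diet term, "we will use a two-sided likelihood ratio test to test for no difference between diet types". No covariate measured after randomisation enters this model.

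The end of the same section adds two analyses under the sensitivity label:

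- **Weight.** "we will adjust for baseline weight and percent weight change if weight change from baseline is found to be significant". The reason given is "since this is known to impact HbA1c values".
- **Adherence.** "in a separate analysis, we will adjust for adherence to each diet". This one has no condition attached. The covariate is still to be built: "We will develop a composite score to measure a participant's adherence to each diet".

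The Secondary Outcomes list includes the between-diet difference in percent weight change after 12 weeks of each phase. The SAP does not describe either adjusted model as a mediation or direct-effect analysis. It does not say how a changed diet coefficient is to be read.

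**The concern.** Percent weight change is measured after the diet has started, and the SAP lists it as something the diets may change. The reason given for adjusting, that weight affects HbA1c, makes weight a plausible step on the path from diet to HbA1c. It does not make it a confounder of a randomised within-person comparison.

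Model (1) asks how much HbA1c differs between the diets, by whatever route. Once percent weight change is added, the coefficient asks how much would differ if weight change were the same on both diets. That second question needs an extra assumption, that weight change and HbA1c share no unmeasured cause, and randomisation does not supply it. Adherence has the same structure: it is measured during each diet, and the assigned diet may influence it.

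A sensitivity analysis should address the primary question under other assumptions. If the diets differ partly through weight, a smaller and non-significant adjusted estimate is the expected result. Under the label used, it would read as a sign that the primary finding is not robust.

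**Working it through.** **Inputs from the SAP.** "Forty participants are planned to be randomized between the two arms"; two 12-week diet phases; complete cases only; two-sided tests; "A significance level of 0.05 is set for all analyses". The SAP gives no effect size, SD, dropout rate or power, so it has no figure of its own to reproduce. Every other input below is an assumption.

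**Set-up.** With complete pairs, the diet contrast in model (1) is the mean within-participant difference. Let N be the number of pairs, W the diet difference in percent weight change, b the HbA1c slope per point of weight change, D the direct diet effect, s_w the SD of the weight-change difference and s_h the residual SD of the HbA1c difference.

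- Unadjusted: estimate = D + bW; SE = √(s_h² + b²s_w²)/√N
- Adjusted for the weight-change difference: estimate = D; SE ≈ s_h·√(1/N + W²/((N−1)s_w²))

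**Input set A** (W = −2, b = 0.5, D = −1, s_w = 3, s_h = 4, N = 33; half the effect through weight).

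- Unadjusted: −1 + 0.5(−2) = −2.0; SE = √(16 + 0.25·9)/√33 = 4.27/5.74 = 0.74; ratio 2.7. Simulated: −2.01, significant in 75% of runs.
- Adjusted: −1.0; SE = 4·√(1/33 + 4/(32·9)) = 0.84; ratio 1.2. Simulated: −1.0, significant in 21%.
- At N = 40 the chance of significance falls from 83% to 25%. Random-intercept fits, which are closer to the planned model, gave 82–85% falling to 23–31%.

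**Input set B** (absolute values: W = 2, b = 0.625, D = 1.25, within-participant weight SD 2 so that s_w² = 8, s_h = 4, N = 40; half through weight).

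- Unadjusted: 1.25 + 0.625·2 = 2.50; SE = √(16 + 0.391·8)/√40 = 4.37/6.32 = 0.69; ratio 3.6. Simulated power 0.95.
- Adjusted: 1.25; SE = 4·√(1/40 + 4/(39·8)) = 0.78; ratio 1.6. Simulated estimate 1.24, power 0.34.
- With the whole effect through weight, the simulated estimate goes from 2.46 to about 0.
- With none of it through weight, the estimate stays at 2.50, but the larger SE cuts power from 0.98 to 0.87.

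**How often a real effect would look non-robust** (set B inputs with W varied, mean weight change −7%, total effect 2.5). This is the chance that the primary test is significant, the trigger fires and the adjusted test is not significant, for W from 1 to 3 points:

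| N | half through weight | all through weight |
|---|---|---|
| 40 | 0.40 to 0.71 | 0.45 to 0.88 |
| 32 | 0.39 to 0.69 | 0.37 to 0.81 |

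**Unmeasured common cause.** If a shared cause with SD s adds equally to the weight and HbA1c differences, the adjusted estimate becomes D − W·s²/(s_w² + s²). In set A that is −1 + 2s²/(9 + s²):

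- s = 1: −1 + 2/10 = −0.80
- s = 2: −1 + 8/13 = −0.38
- s = 3: −1 + 18/18 = 0.00

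The true direct effect is −1.0 throughout. In set B with no diet effect on HbA1c at all, a shared cause gave an adjusted estimate of −0.98 and rejection in 23% of runs instead of 5%.

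**The trigger** (N = 40). The SAP does not say whether weight change is tested pooled, per diet, per phase or between diets.

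- Both diets lose 7%: a pooled change-from-baseline test fires in 100% of runs and a between-diet test in 5%. Adjustment then does no harm (2.50 to 2.51, power 0.92 to 0.97).
- Mean change −1%, diet difference 2 points: the pooled test fires in 46% and the between-diet test in 99%.

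**Baseline weight.** Without weight change in the model, adding baseline weight leaves the diet coefficient where it was (2.31 in one mixed-model fit; −1.98 in another set of fits). With percent weight change in a random-intercept model, the weight slope also draws on differences between participants, so baseline weight matters. With baseline weight assumed related to both weight change and HbA1c change, and a true direct effect of −1.0, leaving it out gave −0.61 or −1.63 depending on the inputs. Keeping it gave about −1.05 (−0.92 in a separate run of 150 fits).

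**The case against.** The best defence is that nothing decisive depends on these models. Model (1), its test and its alpha contain no post-randomisation covariate, and no sentence in the SAP lets the adjusted models confirm or overturn the primary result. Whether a diet difference exceeds what weight explains is a fair question, and the SAP says openly why weight is considered. All of the simulated figures rest on chosen inputs. This stands, and it limits the severity. It does not answer the labelling problem, because the SAP calls these sensitivity analyses and gives no rule for reading them.

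Some stronger readings are tempting but not supported:

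- *The trigger makes a real effect look non-robust.* The adjustment does that, chiefly when the diets differ in weight change. A between-diet trigger would select the cases with most attenuation, so changing the trigger alone is no remedy.
- *The trigger tests the wrong quantity.* That follows only if the phrase means change from baseline as such. It may refer to the weight secondary outcome, which is a between-diet contrast. The wording is ambiguous, not shown to be wrong.
- *No test for weight is named.* The model list under the secondary outcomes omits weight, but weight is a listed secondary outcome and the text introduces mixed models and a likelihood ratio test for those outcomes. The list is loose generally: it also omits alpha diversity and adds glucose.
- *The trigger also governs the adherence model.* That model is separate and unconditional.
- *Baseline weight is redundant and can be dropped.* This is true without weight change in the model, but not in the model planned.

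**Conclusion.** The concern holds as a matter of estimand, label and interpretation. Both adjusted models estimate something other than the total diet effect, and that quantity is identified only without unmeasured common causes of the covariate and HbA1c. With half the effect through weight, the estimate halves and the chance of significance falls from about 75–85% to 20–30% in one set of inputs and from 95% to 34% in another. With the whole effect through weight, the adjusted estimate is about zero. These sizes depend on assumed effects, SDs and shares through weight, none of which the SAP supplies. For adherence the structural argument is the same, but the score is undefined and no size can be given.

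The significance condition on the weight model is a lesser defect: it is under-specified, and it makes reporting depend on the data. A reader might infer that the primary result itself is compromised. It is not, since the primary test and alpha are unchanged. The point is minor to moderate.

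**What to change.** Revise the closing sentence of the Primary Analysis section:

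1. Move the weight-adjusted and adherence-adjusted models out of the sensitivity set and present them as explanatory (mechanism) analyses.
2. Run the weight model regardless of any significance test, and report it beside the between-diet difference in percent weight change.
3. Keep baseline weight in that model.
4. State that each adjusted coefficient is a direct effect that assumes no unmeasured common cause of the covariate and HbA1c.
5. State that attenuation after adjustment is not evidence against the primary diet effect.

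The cost is a wording change to the SAP. The adherence model runs as planned, and the weight model now always runs. The downside is that neither counts as a robustness check any longer.

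### The diet-satisfaction test ignores diet order: a shift in ratings between phases costs power and, if the arms also contribute unequal numbers of pairs, favours one diet.

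*SAP*

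**What the plan says.** Under Study Design the SAP states "Forty participants are planned to be randomized between the two arms", the arms being "1) start with 12 week WFKD and switch to 12 week Med-Plus; (2) start with 12 week Med-Plus and switch to 12 week WFKD". Exploratory outcomes lists "Difference in satisfaction with WFKD and Med-Plus diets, using a 5-point Likert scale". The test is fixed near the end of the Primary Analysis section: "we will use a Wilcoxon signed-rank test to evaluate the null hypothesis that the difference between pairs follows a symmetric distribution around zero". The sentence goes on to interpret that null as one "which indicates similar satisfaction with both diets". The same section adds "A significance level of 0.05 is set for all analyses".

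Other outcomes are treated differently. Model (1) for HbA1c has a term for order. The sentence just before the satisfaction test adjusts the secondary outcomes for both order and phase. None of SA1 to SA5 is said to apply to satisfaction; they are introduced because blood draws were delayed.

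**The concern.** The signed-rank test respects the pairing within a participant but treats all pairs as one sample. In a two-period crossover each WFKD minus Med-Plus difference contains the diet effect plus or minus any change in rating from the first to the second phase, and the sign depends on the arm. Novelty, fatigue or changed logistics could all cause such a change. SA5 itself is written "To assess any effect on outcomes due to COVID-19 impact on logistics".

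Symmetry about zero therefore matches equal satisfaction only if there is no phase shift or the arms contribute equal numbers of pairs. The SAP states the equivalence without either condition. At stake is the trial's one comparison of how well participants liked the diets: a real preference for one diet could be missed, and a preference for the other overstated. Because this is a separate test outside the models, adding a phase term to a mixed model would not repair it.

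**Working it through.** **Inputs from the SAP.** Forty participants, two diet orders, a 1 to 5 rating, significance level 0.05. The SAP gives no power, effect size, rating SD or phase shift for satisfaction, so there is no planned figure to reproduce. It states no allocation ratio either; 20:20 is taken as the base case. Two-sided testing is assumed.

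**Algebra.** Let d be the diet effect (WFKD minus Med-Plus), p the phase II minus phase I shift, n1 the pairs with WFKD first, n2 the pairs with Med-Plus first, and N = n1 + n2.

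- Expected difference with WFKD first: d − p. With Med-Plus first: d + p.
- Pooled mean: d + p(n2 − n1)/N.
- Pooled variance with equal arms: about SD² + p².

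*Equal arms.* There is no bias, but there is more spread. Assume d = 0.5 points, an SD of differences of 1.2 and N = 40. Power is then Φ(0.5√40/√(1.44 + p²) − 1.96):
- p = 0: SD 1.20, power 0.75
- p = ±0.5: SD 1.30, power 0.68
- p = ±1.0: SD 1.56, power 0.53

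*Unequal arms, no diet effect, phase II rated 0.5 points lower.* The centre moves towards the diet that the larger arm ate first (here WFKD):
- 22:18: −0.5 × (−4/40) = 0.05 points
- 24:16: −0.5 × (−8/40) = 0.10 points
- 26:14: −0.5 × (−12/40) = 0.15 points

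**Simulation on the 5-point scale.** Latent normal ratings were cut to about 10/15/25/30/20%, with within-person correlation 0.5, a diet effect of 0.5 SD and 10,000 runs per cell. The planned signed-rank test was set against a rank-sum test between arms on phase I minus phase II ratings. Where two figures are given, they are for a preference for one diet or the other.

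| Pairs per arm | Phase shift (assumed) | Signed-rank power | Rank-sum power |
|---|---|---|---|
| 20:20 | none | 79% | 79% |
| 20:20 | 0.5 SD | 73% | 78% |
| 20:20 | 0.8 SD | 61% | 77% |
| 20:20 | 1.0 SD | 51% | 75% |
| 20:16 | 0.5 SD | 77% or 56% | 73% |
| 20:13 | 0.5 SD | 81% or 43% | 68% |

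Type I error of the signed-rank test at a 0.5 SD shift was 3.0% at 20:20, 5.8% at 20:13 and 8.7% at 20:10. At 20:10 with 0.8 SD it was 13.2%. The rank-sum test stayed between 4.6% and 5.5%. With correlation 0.2 at 20:20, the power loss is about 4.5 points at 0.5 SD and about 13 points at 0.8 SD. Repeat runs moved the figures by no more than about 2 points.

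**Different rating assumptions.** With latent SD 1 point, correlation 0.3, centre 3.3, ratings rounded to 1 to 5, a diet effect of 0.5 points and 3,000 runs per cell, the picture is similar. At 20:20 signed-rank power falls from 0.67 (no shift) to 0.61 (0.5 points) and 0.45 (1.0 point), while the rank-sum test stays near 0.66. Signed-rank type I error is at or below 0.05 at 22:18 and about 0.06 at 24:16 with a shift of 0.5 or 1.0 points. At 26:14 it is 0.083 (shift 0.5) and 0.159 (shift 1.0).

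**The case against.** The outcome is exploratory, and no sample size, power claim or decision rests on it. The harm also needs quantities the SAP does not supply. With equal arms the test is only conservative; bias needs a phase shift and unequal arms together. The 20:13 and 20:10 cases assume that one arm loses 35% or 50% of its participants and the other none. For mild shifts little happens: at 20:20 the two tests differ by about 1 point or less at 0.2 SD and about 2 points at 0.3 SD, and at 20:16 type I error stays at 3.2% to 5.1% for shifts up to 0.5 SD. COVID-19 is weak evidence for a common shift, because shelter-in-place was a calendar event that may have met some participants in phase I and others in phase II; the rank-sum test would not remove that for individuals. The SAP also does not say when satisfaction is rated. Finally, a stratified test splits at most 40 people into four cells, and a halved Hodges-Lehmann estimate moves in steps of 0.25 points.

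Most of this stands and sets the weight of the point. It does not rescue the stated reading of the null. Nor is the harm confined to extreme cases: at 20:16 with a shift of only 0.3 SD, signed-rank power is already 77% or 66% depending on which diet is preferred. The worry about stratification is not borne out: the van Elteren version holds its size and costs about 1 point of power (at most 2) against the plain rank-sum test.

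**Conclusion.** The concern holds, as a minor one. The planned test leaves out the order of the diets, and the SAP's unconditional reading of symmetry as similar satisfaction is wrong when a phase shift meets unequal arms. With equal arms and a 0.5 SD shift the cost is about 5 points of power; at 0.2 to 0.3 SD it is 2 points or less. With 20:16 pairs and a 0.5 SD shift, power differs by 21 points (77% − 56%) according to which diet is preferred. Clear inflation of false positives needs marked imbalance, of the order of 26:14 or 20:10. All of these figures rest on assumed shifts, arm sizes and rating distributions, so they show a range and do not predict what will happen in this trial.

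**What to change.** Replace the signed-rank sentence. For each participant compute the first-phase rating minus the second-phase rating, and compare these differences between the two randomised arms with a Wilcoxon rank-sum test, preferably stratified by diabetes versus pre-diabetes status (van Elteren), since randomisation is stratified on it. State the null as no diet difference after allowing for phase. The expected difference is d − p with WFKD first and −d − p with Med-Plus first, so the between-arm shift is 2d. Report half the Hodges-Lehmann shift, with its interval, as the diet effect.

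The cost is one sentence of SAP wording and no new data. If there is in fact no phase shift, power is within about 1 point at equal or near-equal arms, about 2 to 3 points lower at 20:13 (71% to 68%) and about 6 points lower at 20:10. Stratifying costs about 1 further point. The test removes a shift common to all participants; it does not remove calendar-time disruption that fell in different phases for different people.
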